4.0 PROTOCOL

4.1 Purpose and Objectives

The purpose of this study is to develop parameters and assess the safety of the radiofrequency device for a variety of treatments. Treatment results may also be evaluated.

The Primary Objectives are:

- To develop treatment parameters.
- Assess the safety through recording of side effects during course of study.

The Secondary Objectives are:

- Subject satisfaction via continuous verbal feedback during the procedure and at follow up visits.
- Assess the ease of use, patient response, treatment time, functions of the new device.

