4.2 Protocol Summary

Subjects are to be enrolled in this clinical study if they are 18 years of age or older. Up to 225 subjects will be enrolled at 8 study centers. All subjects may receive up to 10 treatments or multiple treatment areas. Subjects will receive a phone call or attend a visit at 2 days and/or 1 week post treatment to record side effects. If a side effect is tracked, the site will continue to call the subject until the event resolves. If deemed necessary by the investigator, the subject may attend an unscheduled visit for side effect assessment. The subject may return for optional follow up visits at 30, 90 and 180 days post last treatment for side effect and efficacy assessments.

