4.3 Protocol Study Design

This investigation is a multi-center, prospective, open label study.

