4.8 Treatment

- Radiofrequency Device Treatment:
 - The type of treatment will determine if gel should be applied to the skin prior to treatment. The gel is a conductive gel created for treatments that use radio frequency (RF) to ensure the proper connection between the hand piece and the skin.
 - A neutral pad will be used in accordance with the operator's manual for the device.
 - The hand piece, applicator or tip will be placed in contact with the skin.
 - The entire defined treatment area will then be treated by delivering energy to the skin.
 - The hand piece, number of passes and parameters used for the treatment will be determined by the Investigator.
 - Parameters may be adjusted throughout the treatment to increase subject comfort.
 - Contact cooling built into the 60mm handpiece may be used to increase subject comfort.
 - Nitronox may be used to increase subject comfort and will be determined by the Investigator.
- Procedural adverse events will be documented.
- Subjects will be asked to report the general level of treatment discomfort/pain on a scale of 0 (none) to 10 (maximum intolerable pain).
- Some subjects may have an incomplete response or no response by the end of the study. At the end of the study treatments using an FDA approved/cleared treatment method may be discussed with the subject and obtained at the cost of the subject.

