16.0 DATA ANALYSIS

All data will be analyzed at the end of the study. The primary analysis will be performed by the intention-to-treat approach. All subjects who begin the treatment is considered to be part of the study whether the subject completes the study or not. Additional per-protocol analysis may also be performed on subjects who complete the entire clinical trial according to the protocol. The most appropriate method of handling missing values will be chosen based on the particular trial's goals, endpoints and context.

Endpoints will be summarized with descriptive statistics. Continuous variables will be summarized with n, mean, standard deviation and range. Frequency counts and percentage of subjects within each category will be presented for categorical data. If applicable, Student's t-test may be used to determine if two sets of data are significantly different from each other and p-values will be reported. If the calculated p-value is below the threshold chosen for statistical significance (0.05, or 0.01 level) then the null hypothesis is rejected in favor of the alternative hypothesis. Subgroup analyses may be performed to identify a subject population that achieves the most benefit. Interim results may also be collected and reported as deemed necessary.

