APPENDIX A:

Protocol Revisions Tracker

[figure not shown]
[figure not shown]
Version Date	Editor	Description
January 6, 2017	[name]	Initial Submission to the IRB
January 12, 2017	[name]	Response to IRB conditional approval;
May 3, 2017	[name]	Add [name] as a study center, increase # of study centers from 1 to 5, increase number of subjects from 50 to 150
November 17, 2017	[name]	Add [name] as a study center Updated FDA clearance, Clarify that the Pelleve and/or TempSure RF Device may be used, update treatment to list that a neutral pad will be used in accordance with the instructions for use, minor administrative edits.
January 19, 2018	[name]	Add [name]. as a study center.
April 9, 2018	[name]	Add [name]. as a study center, add 60mm handpiece as investigational, expansion of subject enrollment (150 to 200) and number of sites (5 to 8), minor administrative edits.
April 25, 2018	[name]	Add adverse event of hardness and nodules.
July 12, 2018	[name]	Added contact cooling may be used during treatment. Added adverse events pertaining to cooling.
October 11, 2018	[name]	Updates/edits to device specifications. Added follow up visits at 2 days and 7 days. Added anesthesia may be used and adverse events. Added additional evaluation methods (user and subject experience, optical coherence tomography, ultrasounds, and a diary). Minor administrative edits
November 12, 2018	[name] / [name]	Update FDA clearance. Update 2 day visit as either a visit or phone call. Add the use of Nitronox and adverse events. Minor admin edits.
November 16, 2018	[name]	Increase number of treatments from 5 to 10. Update to include side effect of loss of pigment in hair.
February 4, 2019	[name]	Add satellite site for [name]. Increase number of subjects from 200 to 225.

March 20, 2019	[name]	Added flexible applicator may be used. Updated TempSure Specifications chart. Admin edits.
----------------	-------------	--------------------------------------------------------------------------------------------

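### The only test Section 16.0 names, Student's t-test, can misstate its error rate in either direction if two independent groups differ in both size and spread; Welch's test removes that at almost no cost (minor).

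*Combined protocol and SAP*

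**What the plan says.** Section 16.0 is mainly descriptive. Continuous variables get n, mean, SD and range; categorical variables get counts and percentages. It then adds: "If applicable, Student's t-test may be used to determine if two sets of data are significantly different from each other and p-values will be reported". The significance level is 0.05 or 0.01, and unnamed subgroup analyses are allowed. No other test is named. The section does not say which sets or outcomes would be compared, whether the test is paired, or which variance form is used.

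On design, Section 4.3 says "This investigation is a multi-center, prospective, open label study". No randomisation, control arm or group quota is described. Section 4.8 says "The hand piece, number of passes and parameters used for the treatment will be determined by the Investigator". Section 4.2 sets the size: "Up to 225 subjects will be enrolled at 8 study centers". The revisions tracker in Appendix A shows the 60mm handpiece entering in April 2018 and, in March 2019, the entry "Added flexible applicator may be used".

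The numeric outcomes that a t-test could reach are pain (0 to 10) and satisfaction (1 to 6), both in Section 4.14.

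**The concern.** Student's two-sample test replaces the two group variances with one pooled value, which is weighted towards the larger group. If the smaller group is the more variable one, the pooled value understates the uncertainty of the difference and p-values are too small. If the smaller group is the less variable one, p-values are too large.

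The design protects against neither case. Handpiece and settings are the investigator's choice, applicators became available at different dates, and subgroups are open-ended, so unequal groups are likely. Nothing makes the spread of pain or satisfaction similar across handpieces either.

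At stake is whether a reported difference in such an outcome, or its absence, reflects the data or the choice of test.

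**Working it through.** **Starting point.** The documents give no power calculation, SD or group size; 225 is an enrolment cap without derivation. There is no stated figure to reproduce, so the check is of the named test's true error rate when there is no real difference.

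**Inputs.** Total N = 225 (Section 4.2) and nominal 5% or 1% (Section 16.0). Assumed, because the documents are silent: two-sided test, two independent groups, normal data, splits of 25/200, 45/180, 75/150 and 112/113, and a ratio r of the smaller group's SD to the larger group's between 0.5 and 2.

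**Formula.** Let the smaller group have size a and SD r, and the larger group size b and SD 1.
- True variance of the difference in means: V = r²/a + 1/b
- Pooled variance: s² = [(a−1)r² + (b−1)]/(a+b−2)
- Variance that Student's test uses: P = s²(1/a + 1/b)
- True error ≈ 2[1 − Φ(c/√(V/P))], with c = 1.971 on 223 degrees of freedom

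**25 vs 200, r = 2.** V = 4/25 + 1/200 = 0.165. s² = (24×4 + 199)/223 = 1.323. P = 1.323 × 0.045 = 0.0595. V/P = 2.77. c/√2.77 = 1.184, so the error is about 23.7%.

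**25 vs 200, r = 0.5.** V = 0.25/25 + 1/200 = 0.015. s² = (24×0.25 + 199)/223 = 0.919. P = 0.919 × 0.045 = 0.0414. V/P = 0.363. c/√0.363 = 3.27, so the error is about 0.1%.

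**Simulation** (200,000 runs per case), Student's test, true error at nominal 5%:

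| Split | r = 2 | r = 1.5 | r = 1 | r = 1/1.5 | r = 0.5 |
|---|---|---|---|---|---|
| 25/200 | 24.0% | 15.0% | 5.0% | 0.8% | 0.1% |
| 45/180 | 17.9% | 12.1% | 5.0% | 1.4% | 0.4% |
| 75/150 | 11.0% | 8.5% | 5.0% | 2.6% | 1.7% |
| 112/113 | 4.9–5.1% in all columns | | | | |

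At nominal 1% the range is from below 0.01% to 12.2%. Welch's test gives 4.9–5.1% at nominal 5% and 0.9–1.1% at nominal 1% in every case. The distortion therefore needs unequal sizes and unequal SDs together.

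**Yes/no data, if anyone tested them this way.** Exact enumeration under equal event rates shows that Student's test on 0/1 values behaves almost like an uncorrected chi-square test.
- 25/200 at nominal 5%: the true error does not exceed 5% (3.7–5.0% at event rates from 0.5% to 50%).
- 25/200 at nominal 1%: 4.6% at an event rate of 0.5%, falling to 1.4% at 5% and about 1% from 10% upwards.
- 45/180 at nominal 5%: 9.0% at an event rate of 0.5%, 8.5% at 1%, 5.4% at 2%, and at or below 5% at 5% and above.
- Welch's test must not be carried over: with unequal groups and event rates of 1–5%, its error at nominal 5% is 7–34%.
- Fisher's exact test, at event rates of 1–50% across the 112/113, 45/180 and 25/200 splits, stays at or below 4.5% at nominal 5% and 0.8% at nominal 1%.

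For illustration, one event in 25 against none in 200 gives Student p = 0.004, whereas Fisher gives 25/225 = 0.11. That is one table, not an error rate.

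**The case against.** The case for leaving the text alone has real force.

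- **The test is optional and loosely described.** It applies only where applicable, no comparison is named, and the pooled form is the usual meaning of the name rather than something the text states. Two sets of data could also be paired, such as satisfaction at 30 and 90 days, and group size then does not matter. This stands, and it limits the point to independent groups.
- **The evidence for unequal spread is thin.** The 120 to 300 W figures in the Section 2.0 specifications are power ceilings, and settings are adjusted for comfort. They say nothing direct about the SD of pain. The SD ratios are assumptions.
- **The 25/200 split is also an assumption.** The cap rose from 200 to 225 in February 2019 and the flexible applicator came in March, but nothing says that those 25 subjects used it. A subject may also have several treatments or areas, so applicators need not define exclusive groups.
- **Confounding is the larger problem.** Groups formed by the investigator's choice may differ in many ways, and no change of test cures that. This stands in full.

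Two stronger readings are tempting. A reader might infer that the primary safety outcome is yes/no and that the plan would apply the t-test to it. The documents do not support this. Section 4.1 says only "Assess the safety through recording of side effects during course of study", Section 9.0 grades severity on three levels, and Section 16.0 gives categorical data counts and percentages. A reader might also infer that imbalance alone spoils the p-value. It does not: with equal SDs the error is 5.0% at every split.

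None of this is a reason to prefer the pooled form. If a p-value from two independent groups is reported, the named test is the less safe of two equally simple options.

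**Conclusion.** The concern holds in a limited form. For numeric outcomes in two independent groups, the only named test can be too liberal or too conservative, and the design prevents neither. Under the assumed splits and SD ratios, the true error at nominal 5% runs from about 0.1% to 24% at 25/200, and from 1.7% to 11.0% at the milder 75/150. With equal SDs or near-equal groups there is no distortion.

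The figures rest on assumed splits, SD ratios and normal data; pain and satisfaction are bounded scales, so they are indicative only. For event percentages, the choice of test matters materially only when events are rare.

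Severity is minor. The study aims to develop parameters and record side effects, its summaries are descriptive, and no conclusion is tied to a test. The point is a cheap improvement to the stated method.

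**What to change.** In Section 16.0, state that:

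- numeric outcomes (for example pain, 0 to 10) in two independent groups of subjects are compared with Welch's unequal-variance t-test;
- if percentages of subjects with an event are tested, Fisher's exact test is used, and no t-test of either form;
- p-values comparing investigator-chosen groups are descriptive, because neither test adjusts for differences between those groups.

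The cost is a few lines of text and no extra data. Welch's test loses negligible power when the SDs are equal. Fisher's test is slightly conservative, and its benefit over a t-test is confined to rare events.

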17.0 REPORTING FOR THE STUDY

A study summary report will be generated. It will include a description of the clinical conduct of the study and results.

18.0 DISCLOSURE

The Principal Investigator and Cynosure employees have signed confidentiality agreements with the sponsor. This confidentiality agreement ensures that all information provided to the Investigator or Data Management and Statistics group dealing with the study and information obtained during the course of the study will be regarded as confidential.

19.0 RESPONSIBILITY OF THE INVESTIGATOR

The Investigator is responsible for ensuring that the clinical study is performed in accordance with the Declaration of Helsinki (revised version of Edinburgh, Scotland, 2000 including notes of clarification, Washington, 2002 and Tokyo, 2004) and FDA Good Clinical Practice Regulations (21 CFR parts 50, 56, and 812). Investigators will supply information to the sponsor such that the sponsor can comply with the Financial Disclosure Rules (21 CFR part 54).

20.0 PROCEDURE FOR AMMENDMENTS TO THE PROTOCOL

No deviations from this protocol will be permitted, except in a medical emergency, without the approval of the Sponsor. Any amendment to this study will be discussed by the Investigator and the Sponsor. If agreement is reached concerning the need for modification, this will be made in a formal amendment to the protocol.

All revisions and/or amendments to the protocol must be approved in writing by the appropriate Institutional Review Board.

21.0 INSTITUTIONAL REVIEW BOARD

This protocol, informed consent forms, and any amendments to the protocol will be reviewed by the appropriate Institutional Review Board prior to initiation. The study will not be initiated without the approval from the Institutional Review Board.

22.0 TERMINATION OF STUDY

The Sponsor reserves the right to discontinue this study for administrative reasons at any time. The Investigator reserves the right to discontinue the study for safety reasons at any time in collaboration with the Sponsor.

23.0 STUDY RECORDS

All records and documents pertaining to the study will be maintained in appropriate permanent files as per the ICH guidelines for Essential Documents for the Conduct of a Clinical Trial and 21 CFR 11, and will be available for inspection by the Sponsor, Sponsor designee, the U.S. Food and Drug Administration or applicable regulatory body at any time.

24.0 DATA SECURITY

To ensure the privacy and confidentiality of data for this protocol, the data will be stored on a restricted access location on a company server. Access to the project directory containing the data will be limited to the Investigators and research staff. Information about data security awareness is promoted through user training and education, supplemented by policies and procedures. Password protection will be used for all transactions that allow viewing, editing, and analysis of data, or that provide access to data fields derived from the original source documents.

25.0 CONFIDENTIALITY OF SUBJECT IDENTIFICATION

After the informed consent has been signed, each subject will be entered on a screening/enrollment log, which will be kept with the study records. Once a subject is consented, a unique subject identification number will be assigned. No two subjects will have the same subject identification number. This subject identification number will identify the subject throughout the study and will be used for all source documents, and Data Collection Forms. The subject identification number will be held confidential so far as permitted by law. Investigative site staff, the Sponsor or its designee, and, under certain circumstances, the FDA and Institutional Review Board (IRB) will be able to inspect and have access to the subject identification number and the confidential data that it links to. Any publication or presentation of data will not contain any identifiable subject information.

APPENDIX A:

Protocol Revisions Tracker

[figure not shown]
[figure not shown]
Version Date	Editor	Description
January 6, 2017	[name]	Initial Submission to the IRB
January 12, 2017	[name]	Response to IRB conditional approval;
May 3, 2017	[name]	Add [name] as a study center, increase # of study centers from 1 to 5, increase number of subjects from 50 to 150
November 17, 2017	[name]	Add [name] as a study center Updated FDA clearance, Clarify that the Pelleve and/or TempSure RF Device may be used, update treatment to list that a neutral pad will be used in accordance with the instructions for use, minor administrative edits.
January 19, 2018	[name]	Add [name]. as a study center.
April 9, 2018	[name]	Add [name]. as a study center, add 60mm handpiece as investigational, expansion of subject enrollment (150 to 200) and number of sites (5 to 8), minor administrative edits.
April 25, 2018	[name]	Add adverse event of hardness and nodules.
July 12, 2018	[name]	Added contact cooling may be used during treatment. Added adverse events pertaining to cooling.
October 11, 2018	[name]	Updates/edits to device specifications. Added follow up visits at 2 days and 7 days. Added anesthesia may be used and adverse events. Added additional evaluation methods (user and subject experience, optical coherence tomography, ultrasounds, and a diary). Minor administrative edits
November 12, 2018	[name] / [name]	Update FDA clearance. Update 2 day visit as either a visit or phone call. Add the use of Nitronox and adverse events. Minor admin edits.
November 16, 2018	[name]	Increase number of treatments from 5 to 10. Update to include side effect of loss of pigment in hair.
February 4, 2019	[name]	Add satellite site for [name]. Increase number of subjects from 200 to 225.

March 20, 2019	[name]	Added flexible applicator may be used. Updated TempSure Specifications chart. Admin edits.
----------------	-------------	--------------------------------------------------------------------------------------------

APPENDIX B:

UNIVERSAL PAIN ASSESSMENT TOOL

This pain assessment tool is intended to help patient care providers assess pain according to individual patient needs. Explain and use 0-10 Scale for patient self-assessment. Use the faces or behavioral observations to interpret expressed pain when patient cannot communicate his/her pain intensity.

WONG-BAKER FACIAL GRIMACE SCALE

ACTIVITY TOLERANCE SCALE	NO PAIN	CAN BE IGNORED	INTERFERES WITH TASKS	INTERFERES WITH CONCENTRATION	INTERFERES WITH BASIC NEEDS	BEDREST REQUIRED
SPANISH	NADA DE DOLOR	UN POQUITO DE DOLOR	UN DOLOR LEVE	DOLOR FUERTE	DOLOR DEMASIADO FUERTE	UN DOLOR INSOPORTABLE
FRENCH	AUCUNE DOULEUR	LÉGÈRE DOULEUR	DOULEUR MODÉRÉE	FORTE DOULEUR	TRÈS FORTE DOULEUR	DOULEUR EXTRÊME
GERMAN	KEINE SCHMERZEN	LEICHTE SCHMERZEN	MÄSSIGE SCHMERZEN	STARKE SCHMERZEN	SEHR STARKE SCHMERZEN	EXTREME SCHMERZEN
JAPANESE	痛みなし	軽い痛み	中程度の痛み	ひどい痛み	非常にひどい痛み	最悪の痛み
